○ is used to indicate a study procedure that does not require documentation in the individual eCRF, but should be confirmed in the patient's source record.

^a The following activities can be performed at a separate visit (maximum 5 days before Visit 1): Informed Consent, Informed Assent, check of inclusion/exclusion criteria, collection of demographic data, recording of Medical History and of height and weight, distribution of subject card. AEs/SAEs leading to withdrawal and SAEs related to study participation or to a concurrent GSK medication/vaccine should also be recorded from the separate visit. Inclusion/exclusion criteria should be rechecked prior to vaccination.

^b Physical examination will be performed only if deemed necessary by the Investigator or delegate.

^c Only for women of childbearing potential.

^d Before blood sample collection, check if there is no contraindication to blood draw.

^e Blood sample collection from Visit 1 will be performed before vaccine administration.

^f Non-medically attended AEs after 28 days post-vaccination are not required to be reported in the eCRF.

Whenever possible, the investigator should arrange study visits within the interval described in [Table 5](#).

Table 5 Intervals between study visits

| Interval | Optimal length of interval | Allowed interval |
|------------------------|----------------------------|------------------|
| Visit 1 → Phone call 1 | 14 days | 11 - 17 days |
| Visit 1 → Visit 2 | 28 days | 21 - 42 days |
| Visit 1 → Phone call 2 | 90 days | 76 - 104 days |
| Visit 1 → Phone call 3 | 180 days | 166 - 194 days |

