8.3. Detecting and recording adverse events, serious adverse events and pregnancies

8.3.1. Time period for detecting and recording adverse events, serious adverse events and pregnancies

All AEs starting within 28 days following administration of the dose of study vaccine (Day 1 to Day 29) must be recorded into the appropriate section of the eCRF, irrespective of intensity or whether or not they are considered vaccination-related.

The time period for collecting and recording SAEs, AEs/SAEs leading to withdrawal from the study, and medically-attended AEs and SAEs will begin at the receipt of study vaccine and will end 180 days following administration of the dose of study vaccine for each subject (at the contact at Day 181). See Section 8.4 for instructions on reporting of SAEs.

All AEs/SAEs leading to withdrawal from the study will be collected and recorded from the time of the receipt of study vaccine(s)/ product(s).

In addition to the above-mentioned reporting requirements and in order to fulfil international reporting obligations, SAEs that are related to study participation (i.e. protocol-mandated procedures, invasive tests, a change from existing therapy) or are related to a concurrent GSK medication/vaccine will be collected and recorded from the time the subject consents to participate in the study until she/he is discharged from the study.

The time period for collecting and recording pregnancies will begin at the receipt of study vaccine and will end 181 days following administration of the dose of study vaccine. See section 8.4 for instructions on reporting of pregnancies.

An overview of the protocol-required reporting periods for AEs, SAEs, and pregnancies is given in [Table 11](#).

Table 11 Reporting periods for collecting safety information

| | V1 | | Phone call 1 | V2 | Phone call 2 | Phone call 3 Study Conclusion |
|--|------------|----|--------------|-----|--------------|-------------------------------|
| | D1 | D7 | D15 | D29 | D91 | D181 |
| Solicited local and systemic AEs | [REDACTED] | | | | | |
| Unsolicited AEs | [REDACTED] | | | | | |
| AEs/SAEs leading to withdrawal from the study | [REDACTED] | | | | | |
| Medically-attended AEs, SAEs | [REDACTED] | | | | | |
| SAEs related to the study vaccine | [REDACTED] | | | | | |
| SAEs related to study participation or concurrent GSK medication/vaccine | [REDACTED] | | | | | |
| Pregnancies | [REDACTED] | | | | | |

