4.2. Secondary endpoints

The following measures will be summarized:

- hSBA GMTs against *N. meningitidis* serogroups A (except Day 29), C, W and Y at Day 1 and at Day 29, for each vaccine group and between-group ratios.
- Within-group ratios of hSBA GMTs against *N. meningitidis* serogroups A, C, W and Y at Day 29 compared to Day 1.
- Percentages of subjects with a ≥ 4-fold rise in post-vaccination hSBA titer for *N*. *meningitidis* serogroups A, C, W and Y at Day 29 compared to Day 1, for each vaccine group and between-group differences.

Note: A 4-fold rise is defined as: a) for individuals whose pre-vaccination titers are < the LOD, the post-vaccination titers must be \geq 4-fold the LOD or \geq the LLOQ whichever is greater; b) for individuals whose pre-vaccination titers are \geq the LOD and \leq the LLOQ, the post-vaccination titers must be at least four times the LLOQ; c) for individuals whose pre-vaccination titers are > the LLOQ, the post-vaccination titers are > the LLOQ.

• Percentages of subjects with hSBA titer ≥8 and ≥LLOQ* against *N. meningitidis* serogroups A, C, W and Y at Day 1 and at Day 29, for each vaccine group and between-group differences.

*Note: To be assessed for each serogroup if the pre-defined LLOQ value for that serogroup is >8.

Safety of the study vaccine formulations will be evaluated for all vaccine groups in terms of the frequency (percentage) of reported adverse events including:

- Any unsolicited AEs reported within 30 minutes after vaccination;
- Solicited local and systemic AEs reported from Day 1 (6 hours) through Day 7 after vaccination;
- Other indicators of reactogenicity (e.g. use of analgesics / antipyretics, body temperature) within 7 days after vaccination;
- All unsolicited AEs reported from Day 1 through Day 29 after vaccination;
- Medically-attended AEs, AEs leading to withdrawal and SAEs reported from Day 1 through Day 181 (during the entire study period).

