This analysis applies to all adverse events occurring during the study, judged either as related or not related to vaccination by the investigator, recorded in AE CRF, with a start date on or after the date of first vaccination. AE starting prior to the first vaccination will only be listed. The original verbatim terms used by investigators to identify adverse events in the CRFs will be mapped to preferred terms using the MedDRA dictionary. The adverse events will then be grouped by MedDRA preferred terms into frequency tables per system organ class (SOC).

All reported adverse events, as well as adverse events judged by the investigator as at least related to study vaccine, will be summarized per SOC and preferred term within SOC. These summaries will be presented by study group and by interval of study observation (with onset from Day 1 through Day 29, during the follow-up period and throughout the study period). When an adverse event occurs more than once for a subject, the maximal severity and strongest relationship to the vaccine will be counted.

205343 (MENACWY CONJ-032 [V59_71]) Statistical Analysis Plan Amendment 1 Final

Separate summaries will be produced for the following categories:

- Adverse events that are related to vaccine
- Unsolicited AEs reported within 30 minutes after vaccination
- Unsolicited AEs reported within 29 days after vaccination
- Adverse events leading to withdrawal
- Adverse events leading to a medically attended visit
- Serious adverse events
- Adverse events leading to Death

Data listings of all adverse events will be provided by subject. In addition, adverse events in the categories above will be provided as listed data (excluding Unsolicited AEs reported within 29 days after vaccination).

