6.5.2. Additional considerations

Summaries of safety will be presented using frequencies and percentages within each study group. No statistical comparisons among the study groups with respect to any of the safety parameters will be performed.

Incomplete/partial data in the e-Diary (e.g. local and/or systemic reactions reported only for some days and/or for some reactions) will not be considered as protocol deviations. Summary statistics for local and systemic adverse events will not include missing data, hence numerators and denominators may change from day to day and for the different reactions.

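### SAP 6.5.1 tabulates all AEs and all related AEs for the follow-up period and the whole study, although after Day 29 the protocol requires only medically-attended, withdrawal and serious AEs

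*SAP*

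**What the plan says.** **What is tabulated.** The unsolicited-AE part of SAP 6.5.1 opens: "This analysis applies to all adverse events occurring during the study, judged either as related or not related to vaccination by the investigator". It takes what is recorded on the AE form with a start date on or after vaccination. It continues: "All reported adverse events, as well as adverse events judged by the investigator as at least related to study vaccine, will be summarized". The breakdown is by vaccine arm, by system organ class and preferred term, and "by interval of study observation (with onset from Day 1 through Day 29, during the follow-up period and throughout the study period". SAP 6.5.2 sets the form: "Summaries of safety will be presented using frequencies and percentages within each study group". Protocol 10.8.2 speaks only of intervals of observation. The three named intervals come from the SAP and already stand in the SAP of 29 August 2018.

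**What is collected.** Protocol 8.3.1 says: "All AEs starting within 28 days following administration of the dose of study vaccine (Day 1 to Day 29) must be recorded". For the longer period it names fewer events. Collection of "SAEs, AEs/SAEs leading to withdrawal from the study, and medically-attended AEs and SAEs will begin at the receipt of study vaccine" and ends 180 days later, at the Day 181 contact. Footnote f to Table 4 (Protocol 5.5) adds: "Non-medically attended AEs after 28 days post-vaccination are not required to be reported in the eCRF". SAP 6.5.2.3 restates this rule but does not limit any table to it.

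**What the endpoints are.** SAP 4.2, like Protocol 10.2, keeps the two windows apart. One endpoint is "All unsolicited AEs reported from Day 1 through Day 29 after vaccination". The Day 1 to Day 181 endpoint covers medically-attended AEs, AEs leading to withdrawal and SAEs only.

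**The concern.** The tables cross a boundary that the endpoints respect. A reader who sees percentages headed as all AEs, or all related AEs, for the follow-up period and for the whole study will take them as incidence over about five and six months. For events outside the three categories they are not, because nobody was required to record those events after Day 29. A lower follow-up percentage beside the Day 1-29 column could come partly or wholly from the change in collection.

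The late columns may also depend on site practice. Footnote f says other late events need not be entered; it does not say they must not be. Protocol 8.3.3.1 uses an open question about feeling different in any way. Protocol 8.3.3.2.1 asks that AEs reported at a scheduled safety call be entered verbatim, and Protocol 5.6.14.2 schedules such calls at Day 91 and Day 181. One site may enter a minor late event under 8.3.3.2.1 while another omits it under footnote f. SAP 6.5.1 counts whatever is on the form.

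Safety is a secondary objective reported entirely through descriptive percentages, so what those percentages mean matters.

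**Working it through.** **Step 1. Set the tables against the collection rule.** SAP 6.5.1 does not define the follow-up period. I take it as after Day 29 to the last safety call, as Protocol 6.7.1 uses the term.

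| Column in SAP 6.5.1 | AEs required (Protocol 8.3.1; Table 4 footnote f; SAP 6.5.2.3) | What the percentage is |
|---|---|---|
| Day 1-29 | All | All-AE incidence; matches the endpoint |
| Follow-up, Day 30-181 | Medically-attended, withdrawal, serious | One restricted rule, plus volunteered events |
| Whole study, Day 1-181 | All to Day 29, then the three categories | Two rules mixed |

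**Step 2. Count the days (nominal schedule).** Full collection: 29 days. Restricted collection: 181 − 29 = 152 days. Share of the whole-study interval: 152/181 = 0.84.

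**Step 3. Check the denominator.** SAP 11.2 removes a subject only for periods with no available safety data. A subject reached at the Day 91 or Day 181 call has such data and stays in. An uncollected minor event then counts as no event, so the error is downward. For solicited AEs, SAP 6.5.2.2 removes subjects without data to avoid bias towards zero. That section has no counterpart for late unsolicited AEs.

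**Step 4. See whether the shortfall can be sized.** The documents give no AE rates, so there is no plan figure to reproduce. As an illustration on assumptions only, use a constant-hazard model:

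- p = proportion with any unsolicited AE by Day 29; λ = −ln(1 − p)/29
- k = hazard after Day 29 relative to λ
- m = fraction of late AEs in any of the three collected categories
- Follow-up: true 1 − exp(−kλ·152); shown 1 − exp(−m·kλ·152)
- Whole study: true 1 − (1 − p)·exp(−kλ·152); shown 1 − (1 − p)·exp(−m·kλ·152)

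Volunteered events are set to zero. With p = 0.20, λ = 0.2231/29 = 0.00769 per day. Then:

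| k | Follow-up true | Follow-up shown (m = 0.2 to 0.8) | Whole study true | Whole study shown (m = 0.2 to 0.8) |
|---|---|---|---|---|
| 0.25 | 25.4% | 5.7% to 20.9% | 40.3% | 24.5% to 36.7% |
| 1 | 69.0% | 20.9% to 60.8% | 75.2% | 36.7% to 68.6% |

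I then let p run from 0.10 to 0.30 with k at 0.25 or 1 and m at 0.2, 0.4, 0.6 or 0.8.

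- The smallest follow-up gap is 12.9 − 10.5 = 2.4 points (p = 0.10, k = 0.25, m = 0.8). The largest is 84.6 − 31.2 = 53.4 points (p = 0.30, k = 1, m = 0.2).
- The smallest whole-study gap is 21.6 − 19.4 = 2.2 points (p = 0.10, k = 0.25, m = 0.8). The largest is 75.2 − 36.7 = 38.5 points (p = 0.20, k = 1, m = 0.2).

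Every case is downward, but the range is too wide to serve as an estimate.

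**The case against.** The strongest reply is that this is a labelling matter. The SAP says reported events recorded on the AE form, and 6.5.2.3 states the collection rule in the same chapter. Read together, the counts are literally correct. Each prespecified unsolicited-AE endpoint also has a correctly scoped table, because 6.5.1 separately plans summaries of AEs within 29 days, medically-attended AEs, withdrawal AEs and SAEs. Table titles and footnotes sit in mock tables and a table list (SAP 10) that are not in the documents and might already carry a warning. On this view a footnote would do, and it would keep recorded late events in the tables.

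Most of that stands and limits the point. It does not remove it. Nothing in the protocol or SAP limits the late tables or requires a note on them, and a footnote alone would leave percentages of mixed meaning beside the Day 1-29 column.

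A reader might infer more than the documents support:

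- **That both late columns mix two rules.** Only the whole-study column does.
- **That a late AE without medical attention is never required.** AEs leading to withdrawal and SAEs are collected to Day 181 whether or not they are medically attended.
- **That the comparison between vaccines is biased.** The rule is the same in both arms. Allocation is 1:1 with minimization on center (Protocol 5.2.2.2.1), so site habits should fall about evenly. Evaluators are blinded (Protocol 5.3), and SAP 6.5.2 plans no statistical safety comparison.

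**Conclusion.** The point holds as a minor reporting defect. The all-AE and all-related percentages for the follow-up period and the whole study do not estimate all-AE incidence and are not comparable with the Day 1-29 column. This follows from the text and the day count and needs no assumed rate.

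The size stays open. It is tempting to quote a specific understatement, but the figures under Step 4 rest wholly on an assumed early incidence, later hazard and collected fraction. Early unsolicited AEs may include reaction spill-over, since solicited events reported verbally at a visit become unsolicited AEs (Protocol 11.2), so the later hazard could be well below the early one. Volunteered events would narrow the gap by an unknown amount.

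The primary non-inferiority analysis and the planned medically-attended, withdrawal and SAE tables are unaffected.

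**What to change.** In SAP 6.5.1:

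1. Limit the SOC and preferred-term tables of all unsolicited AEs, and of all related unsolicited AEs, to onset Day 1 through Day 29, matching the protocol endpoint.
2. For onset after Day 29 and for the whole study, tabulate only medically-attended AEs, AEs leading to withdrawal and SAEs, with their related subsets. State the collection rule on each table.
3. List any other AE with onset after Day 29, flagging those judged related.

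The cost is SAP wording and a selection flag in the table programs. No new data are needed. The small downside is that volunteered late AEs outside the three categories, including any judged related, appear only in listings; the flag keeps the related ones visible.

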6.5.2. Additional considerations

Summaries of safety will be presented using frequencies and percentages within each study group. No statistical comparisons among the study groups with respect to any of the safety parameters will be performed.

Incomplete/partial data in the e-Diary (e.g. local and/or systemic reactions reported only for some days and/or for some reactions) will not be considered as protocol deviations. Summary statistics for local and systemic adverse events will not include missing data, hence numerators and denominators may change from day to day and for the different reactions.

6.5.2.1. Exclusion of implausible solicited Adverse Event

This section is specific to the use of eDiary card. Exclusion from analyses due to implausible measurements is to be limited to measurements made by study subjects.

Some local and systemic adverse events will be directly measured by the subject and will not be subject to a reconciliation process, even if they are biologically implausible. Therefore, these implausible measurements will be removed from the analysis but included in listings. Implausible measurements are summarized in the table below:

Parameter	Implausible measurements
Body temperature	≤ 33°C or ≥ 42°C
Erythema	For subjects ≥ 6 years: ≥ 900 mm
Induration	For subjects ≥ 6 years: ≥ 500 mm

Table 4 Implausible Solicited Adverse Events

6.5.2.2. Solicited Adverse Events

For details please refer to Section 8.1.3 of the protocol.

Fever, defined as a body temperature of \geq 38°Cirrespective of route of measurement, will be integrated to the summaries as a systemic adverse event.

The analyses will encompass summaries of the data on five levels:

- 1. Daily reports of subjects with solicited adverse events.
- 2. Time of first onset of solicited adverse events (excluding 30 min measurement).
- 3. Solicited adverse events, maximum event severity by event and interval [6h day 3, day 4 -7, and 6h day 7, each without 30 min].
- 4. Duration of solicited adverse events, including ongoing AE after Day 7.
- 5. Solicited adverse events and indicators of solicited adverse events (use of antipyretics and analgesics for treatment or prophylaxis), occurrence of at least one event by category (local, systemic) and interval 6h-Day 3, Day 4-7 and 6h-Day 7, each without 30 min.

For each of the time points or time intervals presented in the summaries, only subjects with at least one plausible observation (i.e., any non-missing values but excluding "Not done/unknown" and implausible values) for the solicited adverse events in the interval of interest will be considered. Subjects without any plausible data (i.e. missing values or reported as "Not done/unknown" and implausible values) will be removed from the denominator to prevent a downward bias (towards zero).

Level 1: Daily reports of solicited adverse event

For each of the time points (6h, days 2, 3, 4, 5, 6 and 7) only subjects with at least one plausible observation (i.e., any non-missing values but excluding "Not done/unknown" and implausible values) for the solicited adverse event in the interval of interest will be considered. Subjects without plausible data (i.e. missing values or reported as "Not done/unknown" and implausible values) will be removed from the denominator in order to prevent a downward bias (towards zero). Data collected will be summarized (frequencies and percentages of subjects) by study group, solicited adverse event and time point.

Level 2: Time of first onset of solicited adverse events

The time of first onset is defined, for each subject, for each solicited adverse event, as the time point at which the respective solicited adverse event first occurred. For erythema, and induration the following threshold will be used: ≥ 25 mm. The summary will provide the frequencies and percentages of subjects with first onset of each solicited adverse events by study group and by each time point (6h, days 2, 3, 4, 5, 6 and 7). Note, 'not done' is treated identical to 'missing'.

CONFIDENTIAL 205343 (MENACWY CONJ-032 [V59_71]) Statistical Analysis Plan Amendment 1 Final Level 3: Solicited adverse events, maximum event severity by event and interval

The maximum event severity will be defined if there is at least one plausible non-missing observation (excluding "Not done/unknown" and implausible values) within this time interval. Each subject's data will be aggregated across the time points of the interval and summarized according to the maximal severity observed for each adverse event, followed by a summary across subjects for each vaccine. Subjects without any solicited adverse events in the interval, i.e., missing values at each of the requested time points, will be removed from the denominator.

Level 4: Number of days with solicited adverse events

The number of days with the adverse event is defined irrespective of severity. This means at least 'mild' solicited adverse event that are assessed qualitatively and ≥ 25 mm for erythema and induration. If a solicited adverse event continues beyond day 7 the period after day 7 is added.

The frequency distribution of the number of days will be provided in a summary table by vaccine and by adverse event.

Level 5: Solicited adverse events, occurrence of at least one event by category (local, systemic) and interval.

The occurrence of at least one solicited adverse event is defined as "any" for a subject if he/she reports greater than "absent" (≥ 25 mm, for erythema and induration) for the respective event and "none" otherwise. The occurrence of at least one solicited adverse event (i.e., none versus any) will be summarized by category (i.e., local, systemic, any), by study group and by time interval.

Use of antipyretics and analgesics for treatment or prophylaxis to treat or prevent pain or fever will be summarized by frequencies and percentages of subjects reporting use of the medications by interval (6h - day 7).

6.5.2.3. Unsolicited Adverse Events

All AEs occurring during the first 29 days after vaccination, including the day of vaccination, and all medically attended unsolicited adverse events, adverse events leading to study withdrawal and serious adverse events occurring at any time during the study will be recorded according to the protocol-specified reporting rules.

Only vaccine-emergent adverse events (see Section 11.2 for definition) will be analyzed, i.e., excluding those after a subject has given informed consent but before vaccination. The selection of unsolicited adverse events and the assignment to time intervals will be done by day of onset and not by days ongoing/persisting.

205343 (MENACWY CONJ-032 [V59_71]) Statistical Analysis Plan Amendment 1 Final

